2.4.5.6 Analyses of vital sign variables

The summary statistics (including number, mean (standard deviation), median, Q1, Q3, minimum and maximum) of all vital signs variables (central laboratory values and changes from Baseline) will be calculated for each planned visit or study assessment (Baseline, each post-Baseline time point, last on-treatment) by treatment group.

The incidence of PCSAs at any time during the TEAE period will be summarized by treatment group for SBP, DBP and HR. All measurements collected during the TEAE period, including unscheduled ones, will be considered for the PCSA summaries. The summaries will include patients in the safety population who have at least one assessment performed during the TEAE period. When a PCSA definition is based on change from Baseline, patients must have a baseline to be included in the summaries.

A listing of patients with at least one post-Baseline PCSA will be provided and will display the patient's profile over time of all vital sign parameters. Individual data listings will include the following flags:

- Baseline values will be flagged "B".
- Parameter values reaching a PCSA limit will be flagged ('+' or '-' depending on the direction).

2.4.5.7 Analyses of electrocardiogram variables

Shift tables will be provided to present ECG status according to baseline status (Normal/Missing, Abnormal) for each treatment group during the TEAE period. Supportive listings of patients with abnormal ECG status at any post-Baseline visit will be provided.

2.4.5.8 Analyses of physical examination variables

Shift tables will be provided to present physical examination findings by body system according to baseline status (Normal/Missing, Abnormal) for each treatment group during the TEAE period. Supportive listings of patients with abnormal findings at any post-Baseline visit will be provided.

2.5 DATA HANDLING CONVENTIONS

2.5.1 General conventions

The following formulas will be used for computation of parameters.

HbA1c

The formula to convert HbA1c from Diabetes Control and Complications Trial (DCCT) aligned value to International Federation of Clinical Chemistry and Laboratory Medicine (IFCC) standardized value is:

$$\text{IFCC-HbA1c (mmol/mol)} = (\text{DCCT} - \text{HbA1c (\%)} - 2.15) \times 10.929.$$

Renal function formulas

The estimated GFR (mL/min/1.73m²) will be calculated using the 4 variable Modification of Diet in Renal Disease (MDRD) formula:

Standard unit: eGFR (mL/min/1.73m²)=

$$175 \times [\text{Serum Creatinine } (\mu\text{mol/L})/88.4]^{-1.154} \times \text{Age (year)}^{-0.203} \times 1.212 \text{ (if Black)} \times 0.742 \text{ (if Female)}$$

Conventional unit: $eGFR(mL/min/1.73m^2) =$

$$175 \times [Serum\ Creatinine\ (mg/dL)]^{-1.154} \times Age\ (year)^{-0.203} \times 1.212\ (if\ Black) \times 0.742\ (if\ Female)$$

Urine ACR

Standard unit: UACR (mg/g) =

$$Urine\ Albumin\ (mg/dL) / (Urine\ Creatinine\ (mmol/L) \times 11.31) \times 1000$$

Conventional unit: UACR (mg/g) = $Urine\ Albumin\ (mg/dL) / Urine\ Creatinine\ (mg/dL) \times 1000$

Calculation of LDL-C

When TG is lower than or equal to 4.52 mmol/L(400 mg/dL), LDL-C is calculated using the Friedewald equation as:

- In Standard unit(mmol/L), $TC - HDL-C - TG/2.17$.
- In Conventional unit (mg/dL), $TC - HDL-C - TG/5$.

2.5.2 Data handling conventions for secondary efficacy variables

Scheduled measurements ([Section 2.5.4](#)) of continuous variables collected during the study will be used in the analysis including those obtained after IMP discontinuation or introduction of rescue therapy. Continuous secondary efficacy endpoints will be analyzed with missing values imputed by the retrieved dropouts or by washout imputation method according to the criterion described in [Section 2.4.4.1](#).

For the categorical secondary efficacy endpoints, data handling conventions are described in [Section 2.4.4.2](#).

2.5.3 Missing data

For categorical variables, patients with missing data are not included in calculations of percentages unless otherwise specified. When relevant, the number of patients with missing data is presented.

Derived variables will be considered missing if any of the original variables required to calculate them are missing. For example, if either a baseline assessment or an endpoint assessment is missing for a particular patient, then change from Baseline at endpoint will be missing. Depending upon the assessment, analyses may not include all patients in the analysis population, because certain patients in the intended population may have missing data.

Incomplete date of first administration of double-blind IMP

Date/time of first administration is the first non-missing start date/time of double-blind IMP

completed in the e-CRF “First dose IMP” module.

For patients who are randomized and dispensed a double-blind treatment kit but who are lost to follow-up just after Visit 3 (eg. only the treatment kit number is reported in the e-CRF “Exposure - treatment period” module without any dose information), the date of first administration will be imputed using the date of randomization. When a patient is randomized but not exposed, “Not taken” should be ticked in the e-CRF “First dose IMP” module.

Handling of computation of treatment duration if IMP end of treatment date is missing

For the calculation of the treatment duration, the date of the last dose of IMP is equal to the date of last administration reported on the end-of-treatment case report form page. If this date is missing, the exposure duration should be left as missing.

The last dose intake should be clearly identified in the case report form and should not be approximated by the last returned package date.

Handling of medication missing/partial dates

No imputation of medication start/end dates or times will be performed. If a medication date or time is missing or partially missing and it cannot be determined whether it was taken prior or concomitantly, it will be considered a prior, concomitant, and posttreatment medication.

Handling of adverse events/hypoglycemia with missing or partial date/time of onset

Missing or partial adverse event/hypoglycemia onset dates and times will be imputed so that if the partial adverse event onset date/time information does not indicate that the adverse event/hypoglycemia started prior to treatment or after the treatment-emergent adverse event period, the adverse event/hypoglycemia will be classified as treatment-emergent. No imputation of adverse event end dates/times will be performed. These data imputations are for categorization purpose only and will not be used in listings. No imputation is planned for date/time of adverse event resolution.

Handling of adverse events when date and time of first IMP administration is missing

When the date and time of the first IMP administration is missing, all adverse events that occurred on or after the day of randomization should be considered as treatment-emergent adverse events. The exposure duration should be kept as missing.

Handling of adverse events/hypoglycemia when IMP end of treatment date is missing

For the purpose of defining TEAE period, the date of the last administration of double-blind IMP is equal to the date of the last administration reported on the e-CRF “Treatment Status Library” page.

If the date of last administration reported on the e-CRF “Treatment Status Library” page is:

- Partially missing, it will be imputed with a date as late as possible before or on the date of last available information on e-CRF “Completion of End of Study/Follow-up”.
- Completely missing, it will be imputed with the date of last available information on e-CRF “Completion of End of Study/Follow-up” page.

If the date of last available information on e-CRF “Completion of End of Study/Follow-up” page is:

- Partially missing, it will be imputed with a date as late as possible.
- Completely missing, all adverse events occurred on or after the first administration of double-blind IMP will be considered as treatment emergent adverse events.

Handling of missing assessment of relationship of adverse events to IMP

If the assessment of the relationship to IMP is missing, then the relationship to IMP has to be assumed and the adverse event considered as such in the frequency tables of possibly related adverse events, but no imputation should be done at the data level.

Handling of missing severity of adverse events

If the severity is missing for 1 of the treatment-emergent occurrences of an adverse event, the maximal severity on the remaining occurrences will be considered. If the severity is missing for all the occurrences, a “missing” category will be added in the summary table.

Handling of potentially clinically significant abnormalities

If a patient has a missing baseline he will be grouped in the category “normal/missing at Baseline.”

For PCSAs with 2 conditions, one based on a change from Baseline value or a normal range and the other on a threshold value, with the first condition being missing, the PCSA will be based only on the second condition.

For a PCSA defined on a threshold and/or a normal range, this PCSA will be derived using this threshold if the normal range is missing; eg, for eosinophils the PCSA is > 0.5 GIGA/L or $>ULN$ if $ULN \geq 0.5$ GIGA/L. When ULN is missing, the value 0.5 should be used.

Measurements flagged as invalid by the laboratory will not be summarized or taken into account in the computation of PCSA values.

Linked adverse events that worsened or became serious

An AE that worsened or became serious will have a separate record in the data from the original event record with an AE identification number that links the new record to the original record. An AE that worsened or became serious will be considered a new recurring AE in the summary of recurrent events or in the summary of events by time intervals.

Handling of missing data for continuous efficacy endpoints

Please See [Section 2.4.4.1](#) and [Section 2.4.4.2](#).

Handling of missing data for categorical secondary efficacy endpoints

Please See [Section 2.4.4.2](#).

Handling of missing data for key secondary safety endpoints

Please See [Section 2.4.5.1](#)

2.5.4 Windows for time points

The following will decide how scheduled and/or unscheduled visits will be used in the analyses on efficacy variables and the by-visit summaries for safety variables (clinical laboratory data in [Section 2.1.4.4](#) and vital signs in [Section 2.1.4.5](#)).

Step 1: A scheduled measurement will be used if available; otherwise, an unscheduled measurement (including the end of treatment/study visit for those prematurely discontinued) will be used if it were on the same date as a scheduled visit;

Step 2: After step 1, if there are still no measurement for a given parameter at a scheduled visit, analysis window below ([Table 3](#)) will be applied to re-allocate a post-Baseline unscheduled measurement to the scheduled visit.

Table 3 – Analyses window definition

Scheduled visit post Baseline	Targeted study day	Analysis window in study days
Week 3 (Visit 4)	21	2 to 31
Week 6 (Visit 5)	42	32 to 62
Week 12 (Visit 6)	84	63 to 104
Week 18 (Visit 7)	126	105 to 153
Week 26 (Visit 8)	182	154 to 227
Week 39 (Visit 9)	273	228 to 318
Week 52 (Visit 10)	364	319 to 419
Week 68 (Visit 11)	476	420 to 538
Week 86 (Visit 12)	602	539 to 664
Week 104 (Visit 13)	728	≥665

Study days are calculated from the day of first administration of double-blind IMP; the day of first administration of IMP (or the day of randomization if not exposed) is Day 1.

After applying the above time windows, if multiple assessments are associated to the same time point, the closest from the targeted study day will be used. In case of equality, the last

measurement will be used. Re-allocated scheduled visits (ie, visit numbers) should be sequential if ordered by the date of measurement.

After Step 2, if there are still no measurement for a given parameter at a scheduled visit, data is considered missing for efficacy analyses, where multiple imputation would be applied as appropriately as described in [Section 2.4.4](#).

Reference day

The reference day for the calculation of extent of exposure, time to onset, and relative days will be the day of the first administration of double-blind IMP or the day of randomization if not exposed to double-blind IMP, denoted as Day 1.

Baseline definition for efficacy/safety data

For the safety analyses, the baseline for a given parameter is defined as the last available measurement (or the average of all measurements for creatinine and eGFR), including unscheduled assessments, assessed prior to the first administration of double-blind IMP. For the efficacy analyses, the baseline for a given parameter is defined as the last available measurement (or the average of all measurements for eGFR), including unscheduled assessments, assessed prior to the first administration of double-blind IMP or the last available value (or the average of all measurements for eGFR) before randomization if not treated with double-blind IMP.

Summary statistics by visit for continuous efficacy endpoints

Summary statistics (number, mean, SD, SE, minimum, median, maximum) of continuous efficacy endpoints (observed data and change from Baseline) will be provided at scheduled visits as per protocol. Summaries showing data by visit will be presented according to the visit number (or re-allocated visit number, see [Section 2.5.4](#)) and labeled with the targeted approximate day/week.

Last on-treatment value for laboratory variables and vital signs

The last on-treatment value is the final measurement assessed during the treatment epoch, regardless of the introduction of rescue therapy, including measurements at unscheduled visits. See [Section 2.1.4](#) and [Section 2.5.4](#) for details.

Display of safety data by visit (laboratory variables and vital signs)

Descriptive statistics (number, mean, SD, minimum, median, maximum) of quantitative laboratory variables and vital signs (observed data and change from Baseline) during the TEAE period will be provided at scheduled visits. In addition, these summaries will also include a row for the 'last value on-treatment' to describe the last available on-treatment value (see above). Summaries showing data by visit will be presented according to the visit number (or re-allocated visit number, see [Section 2.5.4](#)) and labeled with the targeted approximate day/week.

As specified in the study protocol, laboratory data from scheduled visits are reported by central laboratories. The local results will not be used in the efficacy analyses or in the definition of

baseline for both safety and efficacy analyses. In the safety analyses, for parameters with PCSA defined based on normal range, local results will only be used in the PCSA summary if they are accompanied by a local laboratory normal range. For parameters with PCSA not defined based on normal range, local results will be used in the PCSA summary as appropriate.

When a patient has more than one measurement from the central laboratory for the same laboratory parameter on the same date, the average of the measurements will be used. For the same laboratory parameter, if a patient has more than one measurement on different dates for the same scheduled visit, the value closest to the date of the visit will be used for the scheduled visit. When the values for the same scheduled visit are equidistant, the last value should be used for the scheduled visit. Similar rules will be applicable to a patient who has more than one set of measurements for the same vital sign parameter (ie, SBP, DBP, or HR) on the same date.

26-week double blind core treatment period

The 26-week double-blind core treatment period is the time from first administration of double-blind IMP to the last administration of double-blind IMP on or before Visit 8/Week 26 (or Day 182 if Visit 8/Week 26 date is missing). This is for defining EOT status at Week 26 and analyzing selected efficacy parameters (eg, rescued patients) and safety during 26-week core treatment period.

TEAE period for the 26-week double blind core treatment period

The TEAE period for the 26-week double-blind core treatment period is (1) the time from the first administration of the double-blind IMP up to 10 days (1 day for hypoglycemia) after the last administration of IMP if the patient discontinued treatment on or before Visit 8 (or Day 182 if Visit 8 date is missing), or (2) the time from the first administration of the double-blind IMP to the administration at Visit 8/Week 26 (or Day 182 if Visit 8/Week 26 date is missing) if the patient remained treated beyond Visit 8/Week 26. This is for the purpose of safety analyses during the 26-week core treatment period.

26-week core study period

The 26-week core study period is the time from first administration of double-blind IMP to Visit 8/Week 26 (or Day 182 if Visit 8/Week 26 date is missing) or the end of TEAE period for the 26-week double-blind core treatment period (as defined above) whichever is later. This is for defining EOS status at Week 26.

Time to event analysis

For time to event analysis/KM plot, time to event (eg, treatment discontinuation, rescue therapy, hypoglycemia, etc) is defined as the number of days from the date of the first administration of double-blind IMP (or the date of randomization if not exposed) to the start date of the first occurrence of the event during the respective analysis period.

Patients who did not experience any event during the respective analysis period are considered censored observations. The censoring rules are defined below:

Time to event	Censoring date at Week 26 (1st step analysis)	Censoring date at EOT/EOS (2nd step analysis)
Treatment discontinuation due to any reason	Not applicable	EOT
Treatment discontinuation due to AE	Not applicable	EOT
Time to rescue	min (EOT, Date of W26 visit)	EOT
Time to severe or documented hypoglycemia	min (EOT+1, EOS, Date of W26 visit). See Section 3	Min (EOT+1, EOS)

Note: (1) Day 182 will be used if Date of Week 26 visit (or date of W26/re-allocated W26) is not available.

(2) Date of EOS will be used if date of EOT is not available; Last contact date will be used if date of EOS is not available.

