### **10.3.3 List of criteria for permanent treatment discontinuation**

The patients may withdraw from treatment with the IMP if they decide to do so, at any time and irrespective of the reason, or this may be the Investigator's decision. Patients should discuss stopping study medication with the site before doing so, to allow for questions to be addressed, glycemic therapy to be adjusted, and a follow-up assessment to be arranged. All efforts should be made to document the reason(s) for treatment discontinuation and this should be documented in the eCRF.

The following reasons lead to permanent discontinuation:

- At the patient's own request (ie, withdrawal of consent for treatment).
- If, in the Investigator's opinion, continuation with the administration of the study treatment would be detrimental to the patient's well-being.
- Intercurrent condition that requires permanent discontinuation of the study treatment as long as the abnormality persists and if the casual relationship of the concerned event and the IMP is possible (according to the Investigator's best medical judgment).
- BMD decrease of >7% from Baseline.
- Specific request of the Sponsor.

Any abnormal laboratory value or ECG parameter will be immediately rechecked to confirm the result before making a decision of permanent discontinuation of the IMP for the concerned patient.

For patients who prematurely discontinue the IMP, the assessments planned at EOT visit ([Section 1.2](#)) will be performed at the Premature EOT Visit scheduled preferably prior to treatment discontinuation or as soon as possible after the time of discontinuation (at the latest at the next scheduled on-site visit), and a Follow-up Visit 2 weeks ( $\pm 3$  days) after the last dose of IMP. In addition, every effort will be made to have the patient return to the site at the time corresponding to their scheduled visits, particularly the Week 26 Visit and Week 104 Visit. If the patient does not agree to site visits, he or she will be contacted by telephone to inquire about safety status and collect AE data. The reason(s) for IMP discontinuation will be clearly specified. This Premature EOT assessment may occur at a regularly scheduled or at an unscheduled visit.

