1 OVERVIEW AND INVESTIGATIONAL PLAN

1.1 STUDY DESIGN AND RANDOMIZATION

This is a Phase 3, multicenter, randomized, double-blind (single-blind Run-in Phase), placebo-controlled, parallel-group stratified study.

All patients will have a Screening Period comprised of an up to 2-week Screening Phase and a 2-week, single-blind placebo Run-in Phase prior to randomization. Following randomization, patients will have a 104-week double-blind Treatment Period (26-week double-blind core treatment period followed by a 78-week double-blind extension treatment period), and a 2-week post-treatment Follow-up period. Patients who prematurely discontinue the study treatment are expected to continue in the study to continue performing their respective study assessments, especially HbA1c and BMD, until the time of the last visit planned in the protocol.

Patients will be centrally randomized (using permuted block randomization schedule) via an Interactive Response Technology (IRT) in a 1:1:1 ratio to 1 of the 3 treatment groups:

- Sotagliflozin 400 mg.
- Sotagliflozin 200 mg.
- Placebo.

The randomization will be stratified by hemoglobin A1c (HbA1c) at the screening visit ($\leq 8.5\%$, $>8.5\%$) and sex (Male, Female).

It is anticipated to randomize a total of approximately 360 patients (120 per treatment group).

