1.3 DETERMINATION OF SAMPLE SIZE

The sample size/power calculations were performed based on the primary variable of change from Baseline to Week 26 in HbA1c (%).

[figure not shown]
Assuming a common standard deviation (SD) of 1.2% and using a 2-sided test at a 0.05 α -level, 360 patients (120 patients per arm) will have 97% power to detect a treatment difference of -0.6% in mean HbA1c change from Baseline to Week 26 between sotagliflozin 400 mg and placebo.

This sample size will also allow to exclude a decline in BMD from Baseline of $> 2\%$ with a 95% power, assuming a missing rate of 30% and an SD of 3.5%.

The total sample size will be approximately 360 patients to be randomized (120 in sotagliflozin 200 mg group, 120 in sotagliflozin 400 group, and 120 in placebo group).

Calculations were made using East 6.4 software.

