2.4.4.1 Analysis of primary efficacy endpoint(s)

Primary analysis

The primary efficacy endpoint of change in HbA1c from Baseline to Week 26 will be analyzed by an Analysis of Covariance (ANCOVA) model using HbA1c values measured at Baseline and Week 26 (observed or imputed). The missing data at endpoint will be imputed by multiple imputation (MI) methods as detailed below. To be concise, the following texts related to imputation are generalized to accommodate primary as well as continuous secondary efficacy endpoints.

Missing endpoint data at Week 26 (or Week 12 for SBP) visit will be imputed using a model built separately in each treatment group and estimated from the patients in the same treatment group who prematurely discontinue the IMP before the Week 26 (or Week 12 for SBP) visit but have the measurement for the endpoint (ie, retrieved dropouts). The imputation model will include the randomization strata and the corresponding baseline value. In cases of non-convergence during the imputations, the offending stratum will be identified and then will be dropped from the model. Considering that the number of retrieved dropout patients in each treatment group is expected to be small, a simple imputation model based on regression will be used with baseline measurement included as the predictor. This will serve as the primary method of imputation for missing data should sampling criteria be satisfied (see below).

An alternative (back-up) imputation method will be used if the number of patients who prematurely discontinue the IMP before the Week 26 (or Week 12 for SBP) visit but have the measurement for the endpoint is < 5 in any treatment groups (ie, an insufficient number of retrieved dropouts to support the imputation method described above). This criterion will be assessed for each primary or continuous secondary efficacy endpoint.

In the back-up imputation method, missing post-Baseline endpoint values at Week 26 (or Week 12 for SBP) will be imputed by the washout Multiple Imputation (MI) method under the missing not at random (MNAR) framework.

Missing endpoint data at the Week 26 (or Week 12 for SBP) in all treatment groups (sotagliflozin 400 mg, sotagliflozin 200 mg and placebo) are imputed from a model estimated from patients in the placebo group who have the endpoint data available.

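### A premature end-of-treatment value taken on drug can be windowed to Week 26 and then serve as a retrieved-dropout donor and count toward the five-donor minimum

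*SAP*

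**What the plan says.** SAP 2.4.4.1 imputes a missing Week 26 value (Week 12 for SBP) from a regression fitted separately in each arm. The donors are patients who stopped IMP before that visit "but have the measurement for the endpoint (ie, retrieved dropouts"). If any arm has fewer than five of them, the washout method, which draws on placebo data, replaces it.

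SAP 2.4.4 refers to SAP 2.5.4 for what counts as missing. Step 1 there uses a scheduled value if there is one. Otherwise "an unscheduled measurement (including the end of treatment/study visit for those prematurely discontinued) will be used", on condition that it shares its date with a scheduled visit. If there is still no value, Step 2 says the analysis window "will be applied to re-allocate a post-Baseline unscheduled measurement to the scheduled visit". The windows are Days 154 to 227 for Week 26 (target 182) and Days 63 to 104 for Week 12 (target 84). A value is missing only if both steps find nothing.

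Protocol 10.3.3 says the EOT assessments "will be performed at the Premature EOT Visit scheduled preferably prior to treatment discontinuation or as soon as possible after the time of discontinuation". The following on-site visit is the outer limit, and the assessment may be made at an unscheduled visit. The EOT panel in Protocol 10.1.3.2 includes HbA1c.

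**The concern.** A retrieved-dropout model is useful because its donors show what happens after treatment stops. Take a patient who has an EOT HbA1c on Day 160 while on drug, stops, and does not return. Step 2 gives this patient a Week 26 value. The patient also stopped before Week 26, so both parts of the donor definition are met, although the value says nothing about the period after stopping.

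Two things follow. On-drug donors pull the imputed values in a sotagliflozin arm toward the treated mean, and the SAP itself expects donors to be few. The same patients also count toward the minimum of five, so the washout back-up may not be triggered when too few real post-discontinuation values exist.

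**Working it through.** **Plan's own figure.** SAP 1.3: "Assuming a common standard deviation (SD) of 1.2% and using a 2-sided test at a 0.05" level, 120 patients per arm "will have 97% power to detect a treatment difference of -0.6% in mean HbA1c change from Baseline to Week 26". A two-sample normal calculation gives 0.972 (noncentral t: 0.971), so 97% reproduces and is not disputed. The only missing rate in the documents is for BMD ("assuming a missing rate of 30% and an SD of 3.5"). No rate of stopping or of return at Week 26 is given for HbA1c, so everything below is conditional on assumptions.

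**Assumptions.**
- A fraction d of each arm stops before Week 26, spread evenly over Days 1 to 181.
- A fraction r of all stoppers, early or late, returns for a scheduled Week 26 value.
- Every non-returner who stops on Days 154 to 181 has an on-drug EOT value in the window.
- The on-drug effect is -0.6, and it is 0 in donors measured after stopping.

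**On-drug share of donors.** The share of stoppers in the window is w = 28/181 = 0.155. Off-drug donors number R = 120dr, windowed EOT donors c = 120d(1-r)w. The on-drug share is q = c/(c+R) = w(1-r)/[w(1-r)+r]:
- r = 0.3: 0.108/0.408 = 26.5%
- r = 0.5: 0.077/0.577 = 13.4%

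**Shift from donor contamination.** Patients still missing number m = 120d(1-r)(1-w). The shift is 0.6 × q × m/120:

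| d | r | m | q | shift (HbA1c points) |
|---|---|---|---|---|
| 0.10 | 0.5 | 5.1 | 0.134 | 0.003 |
| 0.10 | 0.3 | 7.1 | 0.265 | 0.009 |
| 0.20 | 0.3 | 14.2 | 0.265 | 0.019 |
| 0.30 | 0.5 | 15.2 | 0.134 | 0.010 |
| 0.30 | 0.3 | 21.3 | 0.265 | 0.028 |

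The largest is 0.028/0.6, about 5% of the assumed effect. A fixed-count example: 5 donors, 3 of them on drug, and 10 missing of 120 move the donor mean by 0.6 × 3/5 = 0.36 and the arm mean by 0.36 × 10/120 = 0.03.

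**The five-donor gate.** The number of donors per arm is binomial with n = 120. Its probability is d[r + (1-r)w] as written and dr with off-drug donors only. The chance of at least five is cubed for three independent arms:

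| d | r | as written | off-drug only |
|---|---|---|---|
| 0.10 | 0.3 | 0.16 | 0.03 |
| 0.15 | 0.3 | 0.65 | 0.25 |
| 0.20 | 0.2 | 0.72 | 0.15 |
| 0.20 | 0.5 | 0.996 | 0.98 |

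The gap is wide when off-drug donors number around five per arm and closes when they are plentiful.

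**SBP at Week 12.** The matching span is Days 63 to 83, or 21/83 = 25% of pre-visit days. Blood pressure is also taken at the follow-up visit 14 days after the last dose. SAP 2.5.4 takes the value nearest the target and gives ties to the later one. For a stop on Day s with an EOT value that day, the follow-up value wins if |s + 14 - 84| ≤ 84 - s, that is, s ≤ 77. If follow-up values count as re-allocable, the on-drug EOT value survives only for Days 78 to 83 (6/83 = 7%). HbA1c is not measured at follow-up, so it has no such protection.

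**The case against.** The route is narrow. Step 1 alone does not move an EOT value to Week 26; only Step 2 does, and only without a scheduled value. Return at Week 26 is specifically sought, some EOT visits will follow the last dose, and EOT values before Day 154 go to earlier visits. All of this stands and limits the number of patients affected.

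The estimand uses all data whether or not IMP was stopped, and no washout is required. A patient who stops on Day 175 and attends on Day 182 has a legitimate observed value. This also stands, and it rules out any remedy that discards scheduled values.

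Protocol 9.4 says HbA1c reflects the previous 120 days. A reader might infer that each late stopper's own windowed value is also wrong by the full 0.6. The documents do not support that: with at most 28 days off drug by Day 182, most of the effect would still show. The working therefore counts only values carried into the imputation of others. The same memory makes the zero effect assumed for off-drug donors too stark, so the shifts shown lean high on that account.

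The planned sensitivity analyses help in part. If retrieved-dropout imputation is primary, the washout analysis is also presented and uses no active-arm donors. The tipping-point analysis penalises imputed values only. Both still treat windowed EOT values as observed, and neither changes which method is primary.

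**Conclusion.** The gap is real and minor. The donor definition, the window rule and the EOT timing together allow on-drug values to act as donors and to count toward the minimum of five, and no other provision prevents it. Under the stated assumptions the HbA1c shift is about 0.003 to 0.03 points in the drug's favour. At 20% return, below the range used for the shift, q is 38% and the shift at 30% stopping is 0.6 × 0.38 × 24.3/120 = 0.046. Neither size threatens a trial planned around 0.6 with 97% power.

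The more consequential effect is on the choice of primary imputation method when donors are scarce. The gate probabilities show how often that choice could change; they do not show that the trial's conclusion would.

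Two stronger readings are tempting. One is that Step 1 admits any EOT value as Week 26; its same-date condition says otherwise. The other is that a quarter or more of the donors must be on drug. That would need low return rates, or late stoppers who never return, and the documents state neither. For SBP the effect is probably confined to fewer patients than the window suggests.

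**What to change.** In SAP 2.4.4.1, with a cross-reference in 2.5.4, state three things:

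1. A value makes a patient a retrieved-dropout donor only if it was measured after the last IMP dose by a stated minimum gap. The 10-day residual treatment epoch in SAP 2.1.4 is a ready choice, though for HbA1c it is a minimum given the 120-day memory.
2. A premature EOT value re-allocated by window that fails this condition is not a donor value.
3. The minimum of five is counted on the donors that remain.

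Add that scheduled Week 26 (or Week 12) values stay in the analysis as observed whenever IMP was stopped. The rule governs who informs the imputation; it does not remove scheduled data.

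The cost is a short insertion and a date check in the programming. The downside is fewer donors, so the prespecified washout back-up will be used more often.
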